4.6.3 Study Discontinuation

The Sponsor has the right to terminate this study at any time. Reasons for terminating the study may include, but are not limited to, the following:

- The incidence or severity of adverse events in this or other studies indicates a potential health hazard to patients
- Patient enrollment is unsatisfactory

The Sponsor will notify the investigator if the Sponsor decides to discontinue the study.

4.6.4 Site Discontinuation

The Sponsor has the right to close a site at any time. Reasons for closing a site may include, but are not limited to, the following:

- Excessively slow recruitment

- Poor protocol adherence
- Inaccurate or incomplete data recording
- Non-compliance with the International Council for Harmonisation (ICH) guideline for Good Clinical Practice
- No study activity (i.e., all patients have completed the study and all obligations have been fulfilled)

5. ASSESSMENT OF SAFETY

5.1 SAFETY PLAN

Inavolisib is not approved, and clinical development is ongoing. The safety plan for patients in this study is based on nonclinical and clinical experience with inavolisib in ongoing studies and clinical experience with other PI3K pathway inhibitors. The anticipated important safety risks for inavolisib are outlined below. Please refer to the Inavolisib Investigator's Brochure for a complete summary of safety information.

Several measures will be taken to ensure the safety of patients participating in this study. Eligibility criteria have been designed to exclude patients potentially at higher risk for toxicities due to one or more components of study treatment. Patients will undergo safety monitoring during the study, including assessment of the nature, frequency, and severity of adverse events, with severity graded according to NCI CTCAE v5.0. Safety assessments will include interval history since the previous assessment, physical examinations, and specific laboratory studies. All serious adverse events and adverse events of special interest (AESI) are to be reported in "real time" (within 24 hours of the event) via the electronic data capture (EDC) system. In addition, guidelines for managing adverse events, including criteria for treatment interruption, dosage modification, and/or treatment discontinuation, are provided below.

In addition to the Sponsor's routine and real-time safety monitoring, an iDMC will be established that will operate according to a pre-specified iDMC charter (see Section 3.1.2). As an additional safety monitoring measure, an interim safety review will be performed after the enrollment of the first 25 patients and treatment for at least three cycles.

5.1.1 Identified and Potential Risks Associated with Inavolisib

On the basis of the established class effects of PI3K and mTOR inhibitors in patients with cancer, as well as nonclinical data and clinical experience from Study GO39374 with inavolisib, hyperglycemia, stomatitis/oral mucositis, rash, diarrhea/colitis, and pneumonitis are safety concerns for inavolisib. Given that these adverse events may require either dose interruptions and/or dose reductions or may have the potential to cause life-threatening conditions, close monitoring and a robust risk-mitigation strategy is warranted during the conduct of this Phase III study.

The combinations of inavolisib with palbociclib and letrozole and with palbociclib and fulvestrant are also being explored in Study GO39374. Results to date have shown good tolerability, with no additional safety signals beyond those associated with PI3K inhibitor class-effects and expected toxicities associated with each of the combination partners, palbociclib and letrozole or fulvestrant. Refer to the Inavolisib Investigator's Brochure for details.

5.1.1.1 Hyperglycemia

Effects on glucose and/or insulin metabolism are a known effect with PI3K inhibitors. Increased glucose was observed in rat and dog toxicology studies at all doses tested and appeared to be dose dependent. Hyperglycemia has been reported in patients receiving inavolisib and is an identified risk of inavolisib. Hence, diabetic patients and patients with elevated fasting glucose at baseline (fasting glucose ≥ 126 mg/dL [≥ 7.0 mmol/L] or HbA1c $\geq 6.0\%$ [≥ 42 mmol/mol]) will be excluded from the study. Fasting glucose levels will be assessed at baseline, and fasting glucose levels will be monitored during the study, as outlined in [Appendix 1](#). Patients should be advised to report symptoms associated with hyperglycemia such as polydipsia, polyuria, polyphagia, blurry vision, or symptoms associated with acidosis such as rapid or shallow breathing, confusion, fatigue, headache, or drowsiness.

The preferred first-line agent for the management of hyperglycemia is metformin; more detailed guidelines for study treatment dose modification, interruption or discontinuation ([Table 1](#)), and medical management for patients who experience hyperglycemia ([Table 2](#)) are provided in Section [5.1.2.2](#).

5.1.1.2 Stomatitis and Oral Mucositis

Treatment-related stomatitis/oral mucositis has been reported with the use of inavolisib. Stomatitis has also been reported in $> 10\%$ of patients receiving palbociclib. Therefore, there is a concern for potential overlapping toxicity for the combination of inavolisib and palbociclib. Patients should be advised to report symptoms immediately. Intervention should begin at the earliest signs of oral mucosal inflammation. If locally available, a compounded alcohol-free mouthwash of dexamethasone (0.5 mg in 5 mL) is recommended for prophylaxis or treatment of stomatitis/mucositis. As per the SWISH study (Rugo et al. 2017), patients may use 4 times daily for 8 weeks (10 mL swished for 2 minutes and spat) started concurrently with study treatment, and/or used reactively with the first appearance of symptoms. Additional mouthwash formulations (e.g., combinations of local anesthetic, antihistamine, corticosteroid, antacid, antifungal, and/or antibiotics) or topical corticosteroids (e.g., triamcinolone acetonide 0.05%–0.5%, fluocinolone acetonide 0.025%–0.05%, clobetasol propionate 0.025%) may be implemented. Patients should avoid alcohol, hydrogen peroxide, iodine, or thyme-containing products, as they may exacerbate the condition. They should also avoid harsh mouthwashes (e.g., Listerine). Diet should be modified (e.g., avoidance of spicy foods). Guidelines for managing stomatitis and oral mucositis are provided in [Table 4](#).

5.1.1.3 Potential Gastrointestinal Toxicities

In the 4-week toxicology study of inavolisib in dogs, gastrointestinal inflammation was observed. Thus, patients with inflammatory bowel disease, such as Crohn's disease or ulcerative colitis, and active bowel inflammation (e.g., diverticulitis) will be excluded from this study. Diarrhea, nausea and vomiting have also been reported in > 10% of patients receiving palbociclib. Therefore, there is a concern for potential overlapping toxicity for the combination of inavolisib and palbociclib. Gastrointestinal effects will be closely monitored by interval history and physical examination (see [Appendix 1](#)). Development of abdominal pain, nausea, vomiting, clinically significant changes in stool (e.g., diarrhea, bloody stools) may necessitate more frequent monitoring, and study drug may be held if symptoms are prohibitive for normal function. Clinical evaluation for infectious (e.g., *Clostridium difficile*, enteric bacteria, and cytomegalovirus) or inflammatory (e.g., inflammatory colitis) etiologies for diarrhea should be conducted. Guidelines for managing gastrointestinal toxicities and *inflammatory colitis* are provided in [Table 6](#) and [Table 7](#), respectively.

5.1.1.4 Potential Skin Disorders

Treatment-related rash has been reported for other PI3K inhibitors in clinical studies and is commonly manifested as a maculo-papular rash with or without pruritus. Rash has also been reported in > 10% of patients receiving palbociclib. Therefore, there is a concern for potential overlapping toxicity for the combination of inavolisib and palbociclib. Rash and other dermatologic events should be closely monitored and managed per standard-of-care. Guidelines for management of rash, including dosage modification, are provided in [Table 5](#).

When applicable, ad-hoc photographs of toxicities of the skin or the mucous membranes (i.e., rash or mucositis) may be taken and submitted to the Sponsor to allow further evaluation.

5.1.1.5 Potential Lung Inflammation/Pneumonitis

Lung inflammation was observed in the inavolisib 4-week dog study at the highest dose tested. This finding was observed only at a dose level considered not tolerable in this species. Interstitial lung inflammation/pneumonitis has been observed in clinical studies with other PI3K inhibitors. Rare but severe lung inflammation has been reported with CDK4/6 inhibitors, including palbociclib, when taken in combination with endocrine therapy. Across clinical trials (PALOMA-1, PALOMA-2, PALOMA-3), any grade and Grade ≥ 3 events of interstitial lung disease (ILD)/pneumonitis were reported in 1.0% and 0.1% of patients treated with palbociclib, respectively. Although no fatal cases were reported from these studies, additional cases of ILD/pneumonitis with fatalities have been observed in the post-marketing setting. Therefore, there is a concern for potential overlapping toxicity for the combination of inavolisib and palbociclib. Specific management guidelines and guidance for holding or discontinuing therapy for symptomatic and asymptomatic pneumonitis based on the severity of pneumonitis are provided in [Table 8](#).

5.1.1.6 Potential Immunosuppressant Effects

Immunosuppression and increased risk of infections are known to be associated with marketed PI3K-mTOR pathway inhibitors. Toxicology studies demonstrated decreases in reticulocytes, leukocytes, and absolute lymphocyte counts in animals treated with inavolisib. Thus, patients who are immunocompromised as the result of HIV or receiving immunosuppressive therapies will be excluded from this study. Patients will be monitored routinely for changes in circulating blood counts, including white cell differential, and should be monitored for fever and signs of infection.

5.1.1.7 Potential Reproductive Effects

Potential adverse effects on male reproductive function, including focal inspissation of seminiferous tubule contents and multinucleated spermatids in the testis and epithelial degeneration/necrosis in the epididymis, were observed in one or more dogs in the 4-week repeat-dose toxicity study. Focal inspissation of seminiferous tubule contents persisted in one animal at the end of the 4-week recovery period.

Patients should be notified of the possibility of reproductive sterility. In the event of patient concern and in accordance with local standards, Principal Investigators may opt to refer male patients for consultation with a local sperm preservation facility (i.e., sperm bank). Because of the unknown effects on human reproductive organs and gonadal cells, all male and female patients should use an effective means of contraception (e.g., abstinence, double-barrier method, surgical sterilization of partner) while taking inavolisib.

5.1.1.8 Potential Ocular Toxicities

In the 4-week toxicology study in rats, lens degeneration was observed in the highest inavolisib dose group (10 mg/kg; 4 of 30 rats). This finding was characterized by minimal-to-mild lens fiber swelling, separation of lens fibers and/or accumulation of subcapsular proteinaceous material. It is unclear whether the lens finding was a direct effect of inavolisib or an indirect effect secondary to marked hyperglycemia in this dose group. No inavolisib-related eye findings were observed in rats at lower doses. In dogs, ocular-related findings included inflammation and lens fiber swelling. In dogs administered 1.5/1.0 mg/kg inavolisib for 3 months, ocular inflammation was limited to focal, minimal neutrophilic infiltrates in the stroma of the corneal-limbal junction of the eye. In the 4-week study in dogs, neutrophilic infiltration in limbus and sclera, mild endophthalmitis, and low-grade uveitis were observed in the highest dose group (treated with 5 mg/kg and reduced to 3 mg/kg), a dose that was not considered tolerable. These findings were reversible and likely part of a systemic generalized inflammatory condition. In dogs administered ≥ 0.3 mg/kg inavolisib in the 3-month toxicity study, bilateral, reversible, very slight swelling of the fibers at the equatorial region of the lens was observed in one male and one female at 0.3 mg/kg, and one male and one female at 1.5/1.0 mg/kg. Although lens fiber swelling may be a result of changes in lens osmotic pressure associated with hyperglycemia present at 1.5/1.0 mg/kg in this study, since hyperglycemia was not observed in animals at 0.3 mg/kg, a direct inavolisib effect

cannot be ruled out. The clinical relevance of these ocular findings to humans is unknown.

Patients with any concurrent ocular or intraocular condition, such as cataract or diabetic retinopathy, that would require medical or surgical intervention during the study period to prevent or treat vision loss, will be excluded from the study. In addition, patients with active uveitis or vitritis, history of uveitis, or active infectious process in the eye will also be excluded from the study. Patients will undergo ophthalmic examinations at baseline during the screening period, at Cycle 6 during the study treatment period, at study treatment discontinuation, and based on any ocular disturbances. The ophthalmic examination should consist of a full ophthalmic exam with dilation and refraction with specific attention paid to lens examination and detailed documentation. During study treatment, hyperglycemia will be managed according to the guidelines in [Table 2](#). In addition, patients will be asked if they have experienced any significant visual changes, pain, or sensitivity to light at each clinic visit. Any new eye-related symptoms including significant change in vision, eye pain, or photophobia will be evaluated by an ophthalmologist.

5.1.1.9 Drug–Drug Interactions

In vitro data suggest that inavolisib is metabolized by CYP3A4 and that there is a low-to-moderate potential for DDI with any medication that strongly inhibits or induces this enzyme. In addition, in vitro data suggest that inavolisib is a substrate of the efflux transporter P-glycoprotein. Palbociclib is extensively metabolized by CYP3A4. Co-administration of a strong CYP3A inhibitor (itraconazole) increased the plasma exposure of palbociclib in healthy subjects by 87%, and co-administration of a strong CYP3A inducer (rifampin) decreased the plasma exposure of palbociclib in healthy subjects by 85%. Therefore, strong CYP3A4 inhibitors and inducers are prohibited in this study (see [Section 4.4.3](#)).

5.1.2 Management of Patients Who Experience Adverse Events

5.1.2.1 Dose Modifications of Inavolisib/Placebo

The inavolisib/placebo dose reduction instructions provided in [Table 1](#) are intended to serve as recommended guidelines to allow ongoing treatment for patients experiencing clinical benefit without signs or symptoms of progression while monitoring patient safety. These guidelines are intended to inform rather than supersede clinical judgment and the benefit-risk balance as assessed by the investigator in managing individual cases. In addition to these guidelines, more conservative drug interruptions or dose reductions for the management of adverse events are permitted at the discretion of the investigator when deemed to be in the best interest of the patient. In general, decisions on interruption of any of the study treatment components (inavolisib/placebo, palbociclib, fulvestrant) should be made independently of the others; that is, one study treatment component alone may be interrupted for adverse events associated with that medication without mandatory interruptions of the other study treatment components.

Dose modification for adverse events should be taken first with inavolisib rather than palbociclib unless clearly attributable to palbociclib alone based on known toxicity profile and the investigator's assessment. When an adverse event is clearly attributed to palbociclib, dose modification of palbociclib alone based on its known toxicity profile and the investigator's assessment is allowed. For toxicities attributed to the combination of inavolisib, palbociclib and fulvestrant, it is preferred to initially modify the dosage of one drug (i.e., inavolisib or palbociclib), then modifying the other drug (e.g., if inavolisib dose was reduced but toxicity persisted or recurred, then reduce the dose of palbociclib), depending upon the nature and severity of the toxicity. Further dose de-escalation may be considered if the same toxicity arises.

Table 1 Overall Dose Modification Guidelines for Inavolisib-Related Adverse Events

	Inavolisib/placebo
Starting dose	9 mg QD
First reduction	6 mg QD
Second reduction	3 mg QD ^a

QD = once daily.

^a If the patient continues to experience specified drug-related adverse events after the second dose reduction, inavolisib/placebo should be discontinued.

The investigator may temporarily suspend inavolisib/placebo dosing due to an inavolisib-related toxicity or an unanticipated medical event not associated with study treatment toxicity or with disease progression. Dose interruptions for any component of study treatment should not exceed one cycle (i.e., approximately 28 days); patients withheld from treatment beyond 28 continuous days are expected to be withdrawn from study treatment. However, the Medical Monitor is available to advise extension for extenuating circumstances. Depending on the nature and the severity of the inavolisib-related toxicity, the investigator may resume inavolisib/placebo dosing in the patient at the same dose or at one dose level lower (as detailed in [Table 9](#)). Dose re-escalation of inavolisib/placebo is permitted only after a thorough benefit-risk evaluation by the investigator; the Medical Monitor is available for consultation as needed.

5.1.2.2 Management of Hyperglycemia

The anti-hyperglycemic agent metformin should be used first-line for the management of sustained fasting glucose > 160 mg/dL or > 8.9 mmol/L or anytime fasting glucose is > 250 mg/dL or > 13.9 mmol/L. Investigators should exercise caution in the dosing and management of patients receiving metformin in combination with inavolisib and must be vigilant for signs of renal impairment and metformin toxicity (see also [Section 5.1.1.2](#)). Patients administered metformin should be cautioned and monitored for signs of intolerance or toxicity, including lactic acidosis, which may occur in the setting of acute

worsening of renal function or cardiorespiratory illness or sepsis and can be life-threatening. The most frequently reported adverse events with metformin are nausea, vomiting, diarrhea, abdominal pain, and loss of appetite. Metformin does not produce hypoglycemia, but it may occur with a missed meal, alcohol consumption, heavy exercise, or when it is taken with another type of diabetes medicine.

In the event metformin is not tolerated or not sufficient, another anti-hyperglycemic medication(s) may be added to or used in place of metformin. Preferred agents include sodium glucose co-transporter 2 (SGLT2) inhibitors, pioglitazone, and dipeptidyl peptidase-4 inhibitors, where available and considered appropriate by investigators. If SGLT2 inhibitors are prescribed, ensure adequate hydration and monitor for vaginal yeast infections. Patients administered pioglitazone should be monitored closely for signs of heart failure including fluid retention or edema. Patients administered insulin or sulfonylureas should be treated with caution when these agents are used to manage hyperglycemia and inavolisib is subsequently interrupted or discontinued: this can lead to rapid escalation of insulin levels and risk of hypoglycemia. For each of these agents, refer to the local prescribing information for additional information.

Patients at risk for developing hyperglycemia (e.g., pre-diabetes, body mass index greater than or equal to 30 kg/m², hemoglobin A_{1c} greater or equal to 5.7%, over 45 years of age, family history of diabetes, history of gestational diabetes, and any other factor that may lead to increased risk of developing hyperglycemia, including certain ethnicities, inactive lifestyle, may initiate treatment with metformin on Day 1 of the study, where allowed by local regulations. [Table 2](#) describes management guidelines of hyperglycemia and [Table 3](#) presents proactive mitigation recommendations for patients with risk factors for hyperglycemia. In addition, any patient may be instructed to utilize a glucometer to monitor fasting glucose at home on a daily basis at the treating investigator's discretion.

Table 2 Management of Hyperglycemia

Fasting Glucose Values	Action to be Taken
>ULN to 160 mg/dL (8.9 mmol/L)	
 • Encourage patients to adopt a diabetic diet. • Consider consultation with endocrinologist or diabetologist. • Provide home glucose monitoring to high risk patients and educate to check fasting glucose at home. ^a • Consider oral anti-diabetic medications (e.g., metformin) for high risk patients. ^a • Recheck in 3 days and adjust medications as needed. ^b • Continue current dose level of inavolisib/placebo.
> 160 to 250 mg/dL (> 8.9–13.9 mmol/L)	
 • Interrupt inavolisib/placebo dose until hyperglycemia resolves to \leq 160 mg/dL or 8.9 mmol/L. ^f • Start or increase dose for an oral anti-diabetic medication (e.g., metformin, SGLT2 inhibitor). ^c • Recheck in 3 days and adjust or add anti-diabetic medications as needed. ^b • Encourage patients to adopt a diabetic diet. • Consider consultation with endocrinologist or diabetologist. • Initiate fasting home glucose monitoring. • Resume current dose level of inavolisib/placebo when hyperglycemia resolves to \leq 160 mg/dL or 8.9 mmol/L. • If fasting blood glucose persists >200–250 mg/dL or > 13.9–27.8 mmol/L for 7 days despite above interventions, discuss with the Medical Monitor. ^f

Table 2 Management of Hyperglycemia (cont.)

Fasting Glucose Values	Action to be Taken

> 250 to 500 mg/dL (> 13.9–27.8 mmol/L)
	
 • Interrupt inavolisib/placebo. • Manage hyperglycemia as per standard-of-care. ^{c, d} • Start or increase dose for an oral anti-diabetic medication (e.g., metformin, SGLT2 inhibitor). ^c • Recheck in 3 days and adjust or add anti-diabetic medications as needed. ^b • Encourage patients to adopt a diabetic diet. • Consider consultation with endocrinologist or diabetologist. • Initiate fasting home glucose monitoring. • If hyperglycemia resolves to ≤ 160 mg/dL or 8.9 mmol/L within 7 days, may resume at current dose level of inavolisib/placebo. • If hyperglycemia resolves to ≤ 160 mg/dL or 8.9 mmol/L in ≥ 8 days, reduce inavolisib/placebo dose by one dose level when treatment resumes. ^e • If hyperglycemia > 250–500 mg/dL or > 13.9–27.8 mmol/L recurs within 30 days, reduce inavolisib/placebo dose by one dose level. ^e

> 500 mg/dL (> 27.8 mmol/L)
	
 • Interrupt inavolisib/placebo. • Manage hyperglycemia as per standard-of-care. ^{c, d} • Assess for volume depletion and ketosis and administer appropriate intravenous or oral hydration. • Start or increase the dose for an oral anti-diabetic medication (e.g., metformin, SGLT2 inhibitor). ^c • Recheck in 3 days and adjust or add anti-diabetic medications as needed. ^b • Encourage patients to adopt a diabetic diet. • Consider consultation with endocrinologist or diabetologist. • Initiate fasting home glucose monitoring. • When hyperglycemia resolves to ≤ 160 mg/dL or 8.9 mmol/L, reduce inavolisib/placebo dose by one dose level when treatment resumes. ^e • If hyperglycemia > 500 mg/dL or > 27.8 mmol/L recurs within 30 days, permanently discontinue inavolisib/placebo.

Table 2 Management of Hyperglycemia (cont.)

SGLT2=sodium glucose co-transporter 2; =ULN upper limit of normal.

- ^a High-risk factors for diabetes include pre-diabetes, overweight, obese, body mass index greater or equal to 30 kg/m², hemoglobin A_{1c} greater or equal to 5.7%, over 45 years of age, family history of diabetes, certain ethnicities, inactive lifestyle, and history of gestational diabetes.
- ^b Fasting glucose should be checked by finger stick or lab value (if patient has scheduled appointment) **PRIOR** to dosing. Oral anti-diabetic medications should be titrated to the maximum allowed dosages to achieve control of blood glucose to ≤ 160 mg/dL or 8.9 mmol/L. For example, metformin may be administered to a maximum dose allowed as per local prescribing information, given in divided doses, as tolerated. Please see local prescribing information of individual oral anti-diabetic agent for dosing guidelines.
- ^c There is a risk of hypoglycemia if insulin or sulfonylureas are used, particularly if these agents are started during periods of inavolisib exposure and doses are not adjusted appropriately during periods of treatment interruption, during which patients' insulin sensitivity may increase rapidly. Short-term insulin is allowed to control blood glucose levels, but goal should be to maintain on oral agents once acute episode resolves.
- ^d It is recommended that the patient is reassessed within 24 hours and preferably the same day for assessments of hydration status and renal function.
- ^e A maximum of two dose reductions will be allowed.
- ^f If, in the investigator's opinion, the benefit-risk assessment favors continued inavolisib dosing without interruption, inavolisib may be continued without interruption upon discussion with Medical Monitor once patients are managed on anti-diabetic agent(s) and fasting glucose ≤ 200 mg/dL [≤ 11.1 mmol/L]. It is recommended that patients be instructed to utilize a glucometer to monitor fasting glucose and to call the clinic if fasting glucose >200 mg/dL [> 11.1 mmol/L] prior to inavolisib dosing at home.

Table 3 Additional Management Guidelines for Patients at High Risk of Hyperglycemia

Patient Characteristics	Guidelines

 • Hemoglobin A1c $\geq 5.7\%$ to $< 6.4\%$ • Pre-diabetes • Body mass index ≥ 30 kg/m² • ≥ 45 years of age • Family history of diabetes • History of gestational diabetes • Any other factor that increases the risk of hyperglycemia (e.g., certain ethnicities such as African American, South Asian; sedentary lifestyle) 	
 • Patient may be instructed to utilize a glucometer to monitor fasting glucose at home on a daily basis at the treating investigator's discretion. • Recommend moderate lifestyle changes such as: 
 Dietary advice (e.g., small frequent meals, low carbohydrate content, high fiber, balanced carbohydrate intake over the course of the day, three small meals and two small snacks rather than one large meal, avoiding drinking sugar-sweetened beverages and switch to water whenever possible) Increase daily physical activity and exercise • Consultation with an endocrinologist or diabetologist is highly recommended. • Consider initiating prophylactic treatment with metformin (on Cycle 1 Day 1) in patients with more than one risk factor, where allowed by local regulations and at the investigator's discretion.

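### In Table 2 (hyperglycemia), the 7-day Medical Monitor trigger pairs >200–250 mg/dL with the next row's mmol/L range; it should read > 11.1–13.9 mmol/L

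*Protocol*

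**What the plan says.** Table 2 in Protocol Section 5.1.2.2 sets site actions by fasting glucose level, with each level given in mg/dL and mmol/L. The second row covers > 160 to 250 mg/dL, which its header equates to > 8.9–13.9 mmol/L. Its actions are to interrupt inavolisib/placebo, start or increase an oral anti-diabetic drug, recheck in 3 days and adjust, advise on diet, consider a specialist consultation, begin home monitoring, and resume the same dose once glucose is at or below 160 mg/dL (8.9 mmol/L). The last bullet adds a discussion with the Medical Monitor, triggered as follows: "If fasting blood glucose persists >200–250 mg/dL or > 13.9–27.8 mmol/L for 7 days despite above interventions".

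Three other places give the conversions needed to read that bullet:

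- The opening paragraph of Section 5.1.2.2 calls for metformin "anytime fasting glucose is > 250 mg/dL or > 13.9 mmol/L".
- The third row of Table 2 is headed > 250 to 500 mg/dL and gives > 13.9–27.8 mmol/L as the equivalent. Its 30-day recurrence rule repeats the same pair.
- Footnote f, which is attached to the disputed bullet, recommends that patients be instructed to "call the clinic if fasting glucose >200 mg/dL [> 11.1 mmol/L] prior to inavolisib dosing at home".

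**The concern.** The bullet offers its two ranges as equivalents, but the mmol/L range starts where the mg/dL range ends. Read in mmol/L, the trigger cannot be met inside its own row: a patient in the row is at or below 13.9 mmol/L, and a patient above 13.9 mmol/L is managed under the next row.

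What would be lost is the only step in the row that brings in the Medical Monitor because glucose has stayed high despite treatment. The row has no dose-reduction rule. The next row does have one, which reduces the dose when recovery takes 8 days or more. Study drug is interrupted in this row, and Section 5.1.2.1 says that "patients withheld from treatment beyond 28 continuous days are expected to be withdrawn from study treatment". A discussion at day 7 leaves up to three weeks to change management before that limit.

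Hyperglycemia is an identified risk of inavolisib (Section 5.1.1.1). In the Phase I study it occurred in 62% of patients, at Grade 3 or higher in 23% (Section 1.3.2). Grade 3 or higher events are of special interest (Section 5.2.3). With about 200 sites worldwide and thresholds printed in both units, the same patient should not be handled differently according to the unit the local laboratory reports.

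**Working it through.** **Conversion factor.** For glucose, mmol/L = mg/dL ÷ 18.016. The protocol's own pairs imply the same factor to rounding:

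| Pair in the protocol | Where | mg/dL ÷ mmol/L |
|---|---|---|
| 126 and 7.0 | Section 4.1.1 | 18.00 |
| 160 and 8.9 | Table 2, row limits and resume threshold | 17.98 |
| 200 and 11.1 | Table 2, footnote f | 18.02 |
| 250 and 13.9 | Section 5.1.2.2, opening paragraph; Table 2 row limits | 17.99 |
| 500 and 27.8 | Table 2 row limits | 17.99 |

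**Printed figure.** The bullet equates >200–250 mg/dL with > 13.9–27.8 mmol/L. This does not reproduce:

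- 200 ÷ 18.016 = 11.10 mmol/L
- 250 ÷ 18.016 = 13.88 mmol/L, which rounds to 13.9

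So >200–250 mg/dL is > 11.1–13.9 mmol/L.

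**Back-conversion of what is printed.**

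- 13.9 × 18.016 = 250.4 mg/dL
- 27.8 × 18.016 = 500.8 mg/dL

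The printed mmol/L range is therefore about 250–500 mg/dL, the range of the third row. The two ranges in the bullet meet only at 250 mg/dL. The lower limit is too high by 13.9 − 11.1 = 2.8 mmol/L (50 mg/dL), far more than rounding could produce.

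**Which unit is right.** The mg/dL range lies inside the row's > 160 to 250 mg/dL, and its lower limit is the 200 mg/dL used in footnote f. The mmol/L range lies wholly outside the row's > 8.9–13.9 mmol/L. So the mg/dL range is the intended one.

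**Band affected.** The values that trigger in mg/dL but not in mmol/L are > 11.1–13.9 mmol/L.

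- In mmol/L: (13.9 − 11.1) ÷ (13.9 − 8.9) = 2.8 ÷ 5.0 = 56% of the row
- In mg/dL: (250 − 200) ÷ (250 − 160) = 50 ÷ 90 = 56% of the row

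**Other thresholds.** All other mg/dL and mmol/L pairs in Table 2 and its footnotes convert correctly, so the fault is confined to this one bullet.

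**The case against.** The error itself is not in dispute: both ranges stand in one continuous sentence of current text, so neither a broken table nor a superseded version explains it. The case on the other side is about weight.

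- **Little is lost.** In this row the drug is already interrupted, oral treatment is started or increased, and glucose is rechecked at 3 days, with correct thresholds in both units. The missing step is a conversation with no prescribed outcome. This stands, and it limits the point to when the Medical Monitor is consulted.
- **The slip is visible.** The row header and the attached footnote f together supply both correct limits, 11.1 and 13.9 mmol/L. A careful reader could work out the right range. Even so, nothing tells the site which of the two printed ranges governs.
- **The ranges are joined by an or.** Taken literally, a patient at 12 mmol/L (12 × 18 = 216 mg/dL) meets the mg/dL limb. The trigger is missed only where a site reads the mmol/L limb alone. The documents do not show that this happened, but sites reporting in mmol/L have little reason to convert.
- **Other safeguards exist.** Footnote f allows dosing without interruption only after discussion with the Medical Monitor and with glucose at or below 200 mg/dL (11.1 mmol/L). The Medical Monitor can also advise on extending an interruption beyond 28 days. These reduce possible harm but do not restore the day-7 prompt.
- **The 56% is a share of the row's numerical width.** It is not a share of patients. The documents give no glucose distribution from which a frequency could be derived.

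**Conclusion.** The point holds. The mmol/L range in the 7-day Medical Monitor trigger is wrong as printed, and the correct one, > 11.1–13.9 mmol/L, follows from the protocol's own figures. The only assumption is that the mg/dL range is the intended one, which the row header and footnote f both support.

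This is a wrong decision threshold in safety guidance for an identified risk, so it should be corrected. It is not a major defect. It bears only on when the Medical Monitor is consulted, and only at sites that act on the mmol/L figure. The rules for interrupting, resuming, reducing and discontinuing inavolisib/placebo are unaffected, as are sample size, alpha, power and endpoints.

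**What to change.** In the last bullet of the > 160 to 250 mg/dL row of Table 2, replace > 13.9–27.8 mmol/L with > 11.1–13.9 mmol/L, and notify sites by a clarification letter. The protocol text could be corrected at the next amendment, but a letter reaches sites sooner. The cost is a one-line correction and the letter. Data collection and analysis do not change.
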